**INVESTIGATOR: [name]**

**FUNDING: Investigator-Initiated Study Grant from Spectranetics**

### Protocol Summary:

Title:	Turbo Power Laser Atherectomy Combined with Drug Coated Balloon Angioplasty for the Treatment of Femoropopliteal De Novo/ Restenotic and In-Stent Restenosis Lesions
Study Objectives:	To determine outcomes of combined Turbo Power laser atherectomy + drug coated balloon (DCB) angioplasty for the treatment of femoropopliteal de novo/restenotic lesions and in-stent restenosis (ISR). Better understanding of these outcomes will help guide optimal treatment algorithms for this difficult to treat cohort of patients.
Primary Endpoint:	Rate of freedom from target lesion revascularization (TLR) at one year
Secondary Endpoints:	
 
• Procedural success (<math>\leq 30\%</math> residual stenosis)
 
• Procedural safety (freedom from significant embolization (sequelae), or dissection)
 
• Freedom from major amputation at 30d, 6mo & 12mo
 
• Freedom from death at 30d, 6mo & 12mo
 
• Freedom from TLR 6 months
 
• Patency at 12 months (up to 20 patients)
 

Study Population:	The intended population will consist of all patients undergoing endovascular treatment of femoropopliteal de novo/restenotic lesions and in-stent restenosis with Turbo Power + DCB treatment.
Design:	This is a retrospective, single-site, non-randomized study.
Sample Size:	Up to 120 patients will be enrolled at Cardiovascular Institute of the South
Treatment	De novo, restenotic or in-stent restenosis lesions treated with Turbo Power Laser atherectomy + Drug-coated balloon angioplasty
Inclusion criteria:	All patients from Cardiovascular Institute of the South who were treated for femoropopliteal de novo/restenotic lesions or in-stent restenosis using Turbo Power laser atherectomy plus drug coated balloon angioplasty between 2016-2017.
Exclusion criteria:	Any incomplete data on procedural approach and treatment.
Duration:	Review of patient data and inclusion into the study is expected to take up to 6 months. Patient data will be included through 12 months post-procedure.
Study start:	Upon receipt of all appropriate approvals and a fully executed contract with the site prior to that site enrolling.

## 1. BACKGROUND INFORMATION

Peripheral artery disease (PAD) is a condition where arteries become narrowed due to plaque and thrombus buildup and this reduces blood flow to the limbs. Millions of Americans are affected by PAD and many more may be asymptomatic. Individuals with PAD have an increased risk for heart disease, aortic aneurysms, stroke and an increased mortality. Due to the prevalence of PAD in society, research is ongoing to help treat this disease.

Percutaneous transluminal angioplasty (PTA) has been one of the most widely used methods of treating PAD; however, it is well known that complications and patency rates are disappointing. Many studies have suggested combining PTA with a debulking therapy could provide better results so there is less tissue compressed. There are many atherectomy devices on the market, but to our knowledge, there is a need to determine the optimal algorithm to best treat PAD.

Excimer laser ablation (ELA) has been performed since 1994 when the first devices received CE mark. There are many devices that modify or remove obstructions in the arteries, but the Excimer laser is unique as it ablates or vaporizes tissue at the catheter tip. The catheter contains optical fibers that transmit pulses of ultraviolet light at 308nm that break down blockages at the molecular level. The laser catheters ablate lesions consisting of plaque, thrombus, neointimal hyperplasia, and calcium.

The Laser Angioplasty for Critical Ischemia (LACI) Registry used excimer laser catheters ranging from 0.9 to 2.5 mm to debulk infrainguinal arteries followed by balloon angioplasty and optional stenting. From visual assessment, baseline lesion stenosis was  $92\% \pm 12\%$  and after laser use, this decreased to  $55\% \pm 24\%$  ( $p < 0.001$ ). 88% of lesions were located in the femoropopliteal arteries.

The CELLO Registry used excimer laser catheters to enlarge the lumen of the superficial femoral artery or proximal popliteal. A 2.0mm Turbo-Elite laser catheter was used to create a pilot channel and the Turbo Booster laser catheter was utilized to increase the lumen diameter. The primary effectiveness endpoint for this study was a decrease of 20% or greater after all laser by core lab assessment. During the study the diameter stenosis was reduced from  $77\% \pm 15\%$  at baseline to  $34.7\% \pm 17.8\%$  post all laser.

The EXCITE Study used Turbo-Elite catheters to create a 2.0 mm pilot channel for Turbo Tandem in femoropopliteal in-stent restenosis (ISR) lesions. Operators could use the Turbo-Elite for multiple passes and enlarging the lumen, but Turbo Tandem was the device used to conduct maximal debulking. This study was randomized to compare ELA + PTA to PTA only with the final mean diameter stenosis by visual assessment at 11.5% vs 18.1% respectively ( $p=0.004$ ). The protocol was amended during the study to collect visual assessment data post Turbo-Elite. In 94 patients, Turbo-Elite effectively reduced baseline stenosis from  $88.3\% \pm 12.2\%$  to  $49.2\% \pm 24.8\%$  with an average mean reduction of  $39.1\% \pm 24.1\%$ . In a post hoc core lab analysis, the baseline stenosis of  $84.8\% \pm 14.7\%$  was reduced to  $58.1\% \pm 13.5\%$  with an average mean reduction of  $26.8\% \pm 14.3\%$ .

While studies have shown the decrease in stenosis with excimer laser atherectomy in a variety of lesion morphologies and arteries, there are no studies specific to Turbo Power laser atherectomy plus drug coated balloon in a variety of lesion morphologies.

## **2. OBJECTIVE(S)**

The objective of this study is to determine outcomes of combined Turbo Power laser atherectomy plus drug coated balloon angioplasty for the treatment of femoropopliteal de novo/restenotic lesions and in-stent restenosis (ISR). Better understanding of these outcomes will help guide optimal treatment algorithms for this difficult to treat cohort of patients.

## **3. DESIGN**

This is a retrospective, single-site, non-randomized study. Up to 120 subjects will be included in this study at Cardiovascular Institute of the South. Patient data will be reviewed through 12 months post-procedure. Out of the 120 patients, up to 20 patients will be included for a sub-analysis of patency. These 20 patients must be compliant with physician discharge instructions to be included in this cohort.

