### **Primary Endpoint:**

Rate of freedom from target lesion revascularization (TLR) at one year

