### **Secondary Endpoints:**

The secondary endpoints consist of:

- Procedural success ( $\leq 30\%$  residual stenosis)
- Procedural safety (freedom from significant embolization (sequelae), or dissection)
- Freedom from major amputation at 30d, 6mo & 12mo
- Freedom from death at 30d, 6mo & 12mo
- Freedom from TLR 6 months
- Patency at 12 months (up to 20 patients)

The device involved in this study is the Spectranetics' Turbo Power laser catheter followed by drug coated balloon angioplasty. These devices are currently available in the United States. The Turbo Power laser catheter is currently indicated for the treatment of peripheral arterial disease including treatment of in-stent restenosis (ISR). Additionally, the two drug-coated balloons on the market in the United States during this retrospective timeframe were IN.PACT Admiral (Medtronic) and Lutonix 035 (CR Bard). They are both indicated for treatment of peripheral arterial disease and specifically, IN.PACT Admiral is indicated for ISR treatment. The present protocol does not involve invasive investigational interventions.

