## 4.2 Inclusion criteria

All patients from Cardiovascular Institute of the South who were treated for femoropopliteal de novo/restenotic lesions or in-stent restenosis using Turbo Power laser atherectomy plus drug coated balloon angioplasty during 2016-2017.

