## 5. SAMPLE SIZE AND STATISTICAL CONSIDERATIONS

**5.1** The study is designed to include up to 120 patients. Descriptive statistics (arithmetic mean, median as indicated, minimum and maximum and standard deviation) will be calculated for continuous variables. Absolute frequencies and percentages will be obtained for qualitative variables. 95% Confidence intervals will be provided. In

calculation of percentages, patients with missing data will not be considered, unless otherwise specified. All baseline characteristics will be summarized. Descriptive statistics will be used to summarize the values and changes from baseline across time.

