## **6. PROCEDURES**

### **6.1 Data Review**

All patients from Cardiovascular Institute of the South who were treated for femoropopliteal de novo/restenotic lesions or in-stent restenosis using Turbo Power laser atherectomy plus drug coated balloon angioplasty between 2016-2017 will be considered for study enrollment.

A review of the study candidate's medical history, procedure and data 12-months post-procedure will be performed and documented on the study CRFs.

Up to 20 patients that have been compliant with the physician's discharge instructions will be included in a subgroup. This subgroup will be specifically reviewed for long-term patency by the duplex ultrasound core lab. These patients will have a duplex ultrasound conducted within 305-425 days post-procedure ( $\pm 60$  days of 12-months post-procedure).

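### 12-month patency is estimated only in patients judged compliant with discharge instructions, an undefined condition that the endpoint label omits and TLR does not share

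*Combined protocol and SAP*

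**What the plan says.** Section 3 sets up the sub-analysis, "Out of the 120 patients, up to 20 patients will be included for a sub-analysis of patency", and attaches the entry condition: "These 20 patients must be compliant with physician discharge instructions to be included in this cohort". Section 6.1 repeats it: "Up to 20 patients that have been compliant with the physician's discharge instructions will be included in a subgroup". It then adds that "This subgroup will be specifically reviewed for long-term patency by the duplex ultrasound core lab", on a scan taken between day 305 and day 425. Section 6.3 gives the same scan window without mentioning compliance.

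The secondary endpoint, in both the Protocol Summary and section 3, reads "Patency at 12 months (up to 20 patients" (closing bracket aside). It discloses the cap but not the compliance condition.

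The rest of the study has no such condition. Section 4.2 admits "All patients from Cardiovascular Institute of the South who were treated for femoropopliteal de novo/restenotic lesions or in-stent restenosis" with the combined treatment in 2016-2017. Section 4.3 excludes only incomplete procedural data. The primary endpoint is "Rate of freedom from target lesion revascularization (TLR) at one year".

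Section 9 defines patency by duplex ultrasound but does not define compliance.

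**The concern.** Following discharge instructions is something a patient does after treatment. Making it an entry condition changes what is estimated: no longer patency after laser plus drug-coated balloon in the treated population, but patency in those who were later judged to have complied. If such patients tend to do better whatever the device, the rate is flattering for the treated population.

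A reader will also naturally set the patency rate beside the TLR rate, although the two describe differently selected patients. In a single-arm descriptive study the estimates are the product, so the population behind each one has to be stated.

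The missing definition adds a second problem. Charts are reviewed retrospectively, and nothing requires compliance to be judged without knowledge of the 12-month outcome. Nothing planned would expose the selection either: the sensitivity analyses in section 8.2 address unresolved missing values only, and no comparison of the 20 with the remaining patients is described.

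**Working it through.** The documents state no patency rate, no compliant share and no derivation of the 20 or the 120, so there is no figure of the plan's own to reproduce. What can be checked is the eligibility text and, on stated assumptions, the possible size.

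**Eligibility compared**

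| | Compliance required? | Source |
|---|---|---|
| Study population | No | Sections 4.2, 4.3 |
| One-year TLR | No | Section 3, Primary Endpoint |
| 12-month patency | Yes, undefined | Sections 3, 6.1 |

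The patency cohort is at most 20/120 = 16.7% of the study. The scan window is internally consistent: 365 − 60 = 305 and 365 + 60 = 425.

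**Gap between compliant-only and all-patient patency**

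Let c be the compliant share, and Pc and Pn the patency in compliant and non-compliant patients. All-patient patency is c·Pc + (1 − c)·Pn, so the compliant-only rate exceeds it by (1 − c)·(Pc − Pn). All inputs are assumptions. With Pc = 80% and Pn = 60%:

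- c = 0.5: 0.5 × 80 + 0.5 × 60 = 70%, a gap of 10 points.
- c = 0.8: 0.8 × 80 + 0.2 × 60 = 76%, a gap of 4 points.

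Over a wider range, c from 0.5 to 0.9 and Pc − Pn from 5 to 30 points, the gap runs from 0.1 × 5 = 0.5 to 0.5 × 30 = 15 points. The sign is positive only because Pc > Pn was assumed.

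**How much deleting the condition would remove**

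Without the condition, the cohort consists of scanned patients, not all patients. They came back for follow-up, so their compliant share is probably higher. Keep 80%/60%, let patency depend on compliance alone, and assume 90% to 95% of scanned patients are compliant:

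- 90%: 0.90 × 80 + 0.10 × 60 = 78%, so 2 points are removed.
- 95%: 0.95 × 80 + 0.05 × 60 = 79%, so 1 point is removed.

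Of a 4-point gap, 2 to 3 points would remain; of a 10-point gap, 8 to 9.

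**Precision, for scale**

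An observed 16/20 (80%) has an exact (Clopper-Pearson) 95% interval of 56.3% to 94.3%. At 96/120 it would be 71.7% to 86.7%. Neither interval reflects selection.

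**The case against.** The strongest reply is that the condition may mean little more than returning for the 12-month ultrasound. The documents do not rule this out. On that reading the scan window already applies nearly the same filter, and deleting the condition changes little. This stands as a limit on size. It does not rescue the text: if the condition means only attendance it is redundant, and if it means more it adds selection that the label does not show.

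Four stronger readings are tempting, and the documents do not support them.

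- *The cohort is defined by good medication adherence.* No section says what the instructions cover.
- *Patency is presented as a whole-population result.* The label gives the cap of 20, section 3 calls this a sub-analysis, and sections 3 and 6.1 state the condition openly. Only the label is silent on compliance.
- *TLR is estimated in everyone.* Section 5.1 drops patients with missing data from percentages, section 4.3 excludes incomplete procedural records, and section 7.2 excludes those who declined consent. The accurate contrast is that TLR carries no compliance condition.
- *The fix would recover the whole 4 to 10 points.* That gap is measured against all-patient patency, which a scan-based cohort does not deliver.

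It is also fair to say that a shift of a few points is small beside an interval from 56% to 94%, that patency is one descriptive secondary endpoint, and that no formal comparison with TLR is planned. These points limit the importance. They do not remove the need to say whom the estimate describes.

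**Conclusion.** The point holds. As written, the plan estimates patency in a subset selected on post-procedure behaviour by an undefined criterion, and the endpoint label does not say so. The result probably overstates patency for the treated population and is not directly comparable with TLR.

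The upward direction rests on the assumption that compliant patients have better patency, and the size rests entirely on assumed inputs. The working gives 4 to 10 points against all-patient patency, of which the change in wording would remove about 1 to 2. The primary endpoint is not affected. This should be corrected, but it limits how one secondary endpoint is interpreted and does not undermine the study.

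**What to change.** In sections 3 and 6.1, delete the compliance condition. Define the patency cohort as included patients with a duplex scan at day 305-425, up to the existing cap of 20, selected without regard to adherence or known outcome, for example consecutively by procedure date.

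Whether or not the condition is kept, tabulate baseline characteristics and one-year TLR for this cohort against the remaining patients, and state that the patency result applies to scanned patients.

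If the condition is kept, define compliance in section 9 and rename the endpoint, in the Protocol Summary and section 3, as patency among compliant patients.

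The cost is a wording change and one extra table from data already collected, with no added patients and no scans beyond the cap. Selection on who is scanned remains. It could act in the other direction if some scans were prompted by symptoms, which is why the table is needed under either option. The patency rate may also look less favourable.

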### **Primary Endpoint:**

Rate of freedom from target lesion revascularization (TLR) at one year

### **Secondary Endpoints:**

The secondary endpoints consist of:

- Procedural success ( $\leq 30\%$  residual stenosis)
- Procedural safety (freedom from significant embolization (sequelae), or dissection)
- Freedom from major amputation at 30d, 6mo & 12mo
- Freedom from death at 30d, 6mo & 12mo
- Freedom from TLR 6 months
- Patency at 12 months (up to 20 patients)

The device involved in this study is the Spectranetics' Turbo Power laser catheter followed by drug coated balloon angioplasty. These devices are currently available in the United States. The Turbo Power laser catheter is currently indicated for the treatment of peripheral arterial disease including treatment of in-stent restenosis (ISR). Additionally, the two drug-coated balloons on the market in the United States during this retrospective timeframe were IN.PACT Admiral (Medtronic) and Lutonix 035 (CR Bard). They are both indicated for treatment of peripheral arterial disease and specifically, IN.PACT Admiral is indicated for ISR treatment. The present protocol does not involve invasive investigational interventions.

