### **8.3 *Confidentiality***

Information about study subjects will be kept confidential and managed according to the requirements of the Health Insurance Portability and Accountability Act of 1996 (HIPAA). Those regulations require a signed subject authorization informing the subject of the following:

- What protected health information (PHI) will be collected from subjects in this study
- Who will have access to that information
- Who will use or disclose that information
- The rights of a research subject to revoke their authorization for use of their PHI.

In the event that a subject revokes authorization to collect or use PHI, the investigator, by regulation, retains the ability to use all information collected prior to the revocation of

subject authorization. For subjects that have revoked authorization to collect or use PHI, attempts should be made to obtain permission to collect at least vital status (i.e. that the subject is alive) at the end of their scheduled study period.

All data and information collected during this study will be considered confidential by the. All data used in the analysis and summary of this study will be anonymous, and without reference to specific subject names. Access to subject files will be limited to authorized personnel of the Investigator, Clinical Site research staff and authorized Regulatory Authorities. Authorized regulatory personnel have the right to inspect and copy all records pertinent to this study

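### Freedom from death has no named vital-status source and leaves out patients of unknown status, so survival is likely to be overstated if deaths are unknown more often than survivors

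*Combined protocol and SAP*

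**What the plan says.** Section 3 lists "Freedom from death at 30d, 6mo & 12mo" among the secondary endpoints. It is the only mortality result in the plan.

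On the source of the data, section 3 says "This is a retrospective, single-site, non-randomized study" and "Patient data will be reviewed through 12 months post-procedure". Section 6.1 adds: "A review of the study candidate's medical history, procedure and data 12-months post-procedure will be performed and documented on the study CRFs". Section 7.2 asks for a waiver of consent because the data are already in existence.

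On missing data, section 5.1 says that in percentages "patients with missing data will not be considered, unless otherwise specified". Nothing elsewhere makes an exception for death, and no time-to-event method or censoring rule is given.

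Three other places bear on the point:

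- Section 8.2 promises efforts to retrieve missing values, and sensitivity analyses where retrieval fails. It does not say what the scenarios are.
- The text on discontinuation in section 4 defines loss to follow-up by failed contacts on three days. It allows contact with a representative or primary care provider and asks for a certified letter.
- Section 8.3 mentions vital status by name, but only for subjects who revoke authorization: "attempts should be made to obtain permission to collect at least vital status".

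**The concern.** For most endpoints a missing value has some cause other than the outcome. For death, the outcome can be the cause. A patient who dies at home or in another hospital may leave a record at the site that simply stops. Under section 5.1 that patient then leaves both numerator and denominator instead of counting as a death.

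Survivors of unknown status are removed as well, and that pushes the percentage the other way. The net error depends on which group is lost more often. It is plausible that deaths are, because a living patient can return to the clinic and a dead one cannot. The documents give no figure that would settle it.

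At stake are the 6- and 12-month survival figures in particular, since records have had more time to stop by then. As the plan stands, a reader of the results could not tell how many patients of unknown status lie behind the percentage.

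**Working it through.** The plan states no expected death rate, loss rate or survival figure, so there is none to reproduce. Section 5.1 says "The study is designed to include up to 120 patients", which is a cap. I use N = 120. All other inputs are assumptions shown over a range.

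**Formula.** Let D be true 12-month mortality, f the share of deaths whose status is unknown, and g the share of survivors whose status is unknown. Under the section 5.1 rule:

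reported freedom from death = (1 − D)(1 − g) / [(1 − D)(1 − g) + D(1 − f)]

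The truth is 1 − D. The two are equal when f = g. The reported figure is too high when f > g and too low when f < g.

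**Results at D = 10% (truth 90.0%)**

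| f | g | Calculation | Reported | Error, points |
|---|---|---|---|---|
| 50% | 10% | 0.81 / (0.81 + 0.05) | 94.2% | +4.2 |
| 25% | 10% | 0.81 / (0.81 + 0.075) | 91.5% | +1.5 |
| 25% | 25% | 0.675 / (0.675 + 0.075) | 90.0% | 0 |
| 10% | 20% | 0.72 / (0.72 + 0.09) | 88.9% | −1.1 |

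With f = 50% and g = 10%, the error is +2.2 points at D = 5% (0.855/0.880 = 97.2% against 95.0%) and +6.1 points at D = 15% (0.765/0.840 = 91.1% against 85.0%).

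**The same in whole patients.** Take 120 patients with 10 true deaths, so the truth is 110/120 = 91.7%. Let 12 survivors be of unknown status, which leaves 110 − 12 = 98 known survivors.

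- 5 deaths unknown: 98/103 = 95.1%, too high by 3.4 points.
- 1 death unknown: 98/107 = 91.6%, about right.
- No death unknown: 98/108 = 90.7%, too low by 1.0 point.

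**What bounds would show.** Assume 6 known deaths among 120.

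| Unknown | Section 5.1 rule | All unknowns alive | All unknowns dead |
|---|---|---|---|
| 6 | 108/114 = 94.7% | 114/120 = 95.0% | 108/120 = 90.0% |
| 12 | 102/108 = 94.4% | 114/120 = 95.0% | 102/120 = 85.0% |
| 24 | 90/96 = 93.8% | 114/120 = 95.0% | 90/120 = 75.0% |

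The section 5.1 figure barely moves as the unknowns increase, while the range of possible truths widens from 5 to 20 points.

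For scale, the exact 95% confidence interval for 108/120 (90.0%) runs from 83.2% to 94.7%. An error of 4 points is a large part of its half-width, and the interval does not allow for it.

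**The case against.** The strongest reply is that the plan is not silent. Section 8.2 covers missing values for every endpoint and promises both retrieval and sensitivity analyses. The discontinuation text gives routes by which a death would be learned. Section 8.4 lists hospital records among source documents. The endpoint is also one of several descriptive secondary results in a single-arm study with no hypothesis test.

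Much of this stands. It limits the weight of the point, and it rules out three stronger readings that a reader might infer.

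- **That survival is certainly overstated, because the rule can only lose deaths.** The rule also removes survivors. The case above with every death known gives 90.7% against a true 91.7%.
- **That deaths come only from one clinic's charts and are pursued only when authorization is revoked.** Section 6.1 does not restrict the review to clinic charts, and the discontinuation text describes wider contact. That text reads as written for prospective follow-up and fits poorly with the waiver design in section 7.2. Its use here is therefore unclear, but it cannot be called absent.
- **That a silent record will be counted as alive.** No rule in the documents says so. The plan does leave undefined when vital status counts as missing.

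The reply does not close the gap. Section 8.2 names no source and no scenario for death, and it leaves the headline percentage under section 5.1. It also helps only if a stopped record is recognised as a missing value. The loss-to-follow-up definition is met by a patient who has died, and it does not require a check for death. Section 8.4 gives general examples of source documents and does not commit the study to a search for deaths.

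**Conclusion.** The point holds in conditional form. The plan does not say how vital status is established at 30 days, 6 months and 12 months, and by default it leaves out patients whose status is unknown. Survival is likely to be overstated if deaths are unknown more often than survivors. That is plausible, but the documents do not establish it.

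The size cannot be computed from the documents. Over the cases in the table at an assumed 10% mortality, the error runs from about −1 to about +4 points. With half of deaths and a tenth of survivors unknown, it is about 2 points at 5% mortality and 6 at 15%. This deserves correction before analysis, at the weight of a descriptive secondary endpoint.

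**What to change.** 1. In section 5.1, exempt death from the missing-data exclusion. Report freedom from death at 30 days, 6 months and 12 months by Kaplan-Meier, censoring at the date last known alive, with the number of unknown status at each time point.
2. In section 8.2, define the scenarios for death: best case with all unknowns alive, worst case with all unknowns dead.
3. In section 6.1, name the vital-status source. For each patient whose record ends before day 365 without a recorded death, check once against available death, referring or primary care records, as far as the IRB waiver permits. Count any death found, with its date.

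The third step is needed because Kaplan-Meier assumes that censored patients have the same risk as those still followed. That fails when the record stops because the patient died, so the method alone does not remove the bias.

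The cost is short text in these sections, a line in the waiver request and a lookup limited to records that stop early. No new patients, visits or procedures are needed. The downside is some clerical time and a survival figure that may be less favourable.
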